## Statistical Analysis Plan

---

## Statistical Analysis Plan

---

### Revision History

Version	Author	Date	Reason for revision
1.0	[name]		Draft

# Statistical Analysis Plan

---

## 1. Trial Summary

The trial is a substantial pragmatic parallel two arm prospective clustered randomised controlled trial to evaluate efficacy of a novel school-based Hindi comic body image intervention in a rural India setting. Schools will be randomised to control or intervention (randomisation with minimisation with target 1:1 with error component). The trial design and its rationale are fully documented in the trial protocol document and in the published study protocol manuscript (Lewis-Smith, H., Hasan, F., Ahuja, L., White, P., & Diedrichs, P. (2022). A comic-based body image intervention for adolescents in semi-rural Indian schools: Study protocol for a randomized controlled trial. *Body Image*).

This document is concerned with the data analysis of the accruing data for the study. The statistical analysis of the study is performed in accordance with the principles stated in the CONSORT guideline statement, with due regard to the SPIRIT guidelines (see Annex 1), and in keeping with Consensus Guideline E9 (Statistical Principles for Clinical Trials) of the International Conference on Harmonisation (ICH).

### 1.1 Objectives

This is a two-group randomised controlled trial with target 1:1 allocation between control arm and an invention arm. Randomisation will be done using minimisation (see Section 3). The intervention has been rigorously developed with the objective of positively affecting body esteem in for both males and females aged between 11 and 14. The primary objectives of the trial are to investigate changes in body esteem within and between the two randomised arms. The secondary objectives are to evaluate changes in negative affect, life engagement, self-esteem, media internalization, and disordered eating both within and between randomised arms. Appropriate validated measures will be measured at baseline, follow-up and 10 weeks after the intervention (see measures and trial schedule).

### 1.2 Participant Measures

Measures are given in Hindi.

The primary outcome measure is the Body Esteem Scale for Adults and Adolescents (BESAA).

The secondary measures are (i) The Positive and Negative Affect Scale (PANAS) (ii) Rosenberg Self Esteem Scale (RSES) (iii) Life disengagement relating to body dissatisfaction using the Body Image Life Disengagement Questionnaire (BILD-Q) (iv) media internalisation using the Internalisation-General subscale from the Socio-Cultural Attitudes To Appearance Questionnaire Scale (SATAQ-3) and (v) disordered eating using the Eating Disorder Evaluation Questionnaire (EDE-Q).

## Statistical Analysis Plan

---

Exploratory measures comprise (i) Skin colour dissatisfaction using a single-item 5-point Likert scale (*How satisfied or dissatisfied are you with the colour of your skin?*) ranging between 1 = Very satisfied to 5 = Very dissatisfied (ii) Body hair dissatisfaction using a single-item 5-point Likert scale (*How satisfied or dissatisfied are you with the amount of hair on your body?*). ranging between 1 = Very satisfied and 5 = Very dissatisfied (iii) Appearance-based teasing using a single-item measure to measure appearance-based teasing (*How often have you been teased about the way you look?*) on a 5-point Likert scale ranging from 1 (*Never*) to 5 (*Always*) (iv) Endorsement of traditional gender roles using a 10-item scale with individual items ranging from 1 (*Strongly disagree*) to 5 (*Strongly agree*).

### 1.2.1 Additional data

Participants will additionally provide data relating to:

- Age
- Gender
- School

## 2 Trial Visit Schedule

The data collection points are summarised in Table 2.1

Procedure	T1 (Baseline)	T2 (5 weeks post T1)	T3 (11 weeks post T2)
Consent	X		
Demographics	X		
BESSA	X	X	X
PANAS	X	X	X
RSES	X	X	X
BILD-Q	X	X	X
SATAQ-3	X	X	X
EDEQ	X	X	X

## Statistical Analysis Plan

---

### 3 Randomisation

Participants will be randomized to either the intervention or control arm at the school level. Randomization will be conducted at the school level to avoid potential spill over effects within a school. Eligible schools will be randomised in a target 1:1 ratio using minimisation with a residual error. The minimisation factors are (i) number of students at grade 6, 7 or 8 and (ii) proportion of boys at grade 6, 7, and 8. The first 8 schools will be allocated using blocked randomisation thereafter probabilistic minimisation will occur with the probability of minimising set to 0.8. Randomisation will be done in the UK.

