### 4 Endpoints

#### 4.1 Primary Endpoint:

To assess whether there are significant differences in body esteem between randomized groups at T2 after controlling for baseline measure of body esteem.

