### 5 Sample Size

The study design comprises two independent groups with data collected at three time points (T1, T2, T3). The resulting data is amenable to standard analysis for two group comparisons including a 2 by 2 by 2 by mixed factorial design with randomised group as a two level between subjects fixed factor, trial phase (T2, T3) as a longitudinal two-level repeated measures factor, gender as a two-level fixed factor and with commensurate baseline measure (T1) as a mean adjusted covariate. This may be assessed as a classic factorial ANCOVA for a 2 by 2 by 2 mixed design or using a random intercepts mixed linear model capturing the full factorial structure. The model will additionally include school as a random factor, and a sensitivity analysis relating to the inclusion-exclusion of this effect will be conducted

The evaluation of *Confident Me* in an urban Indian setting indicated a range of effect sizes for outcome measures with standardized effects in the small to medium range and exceeding an effect size of  $d = 0.2$ , which would minimally be of interest to public health policy makers. For a lower bound of  $d = 0.2$ , a sample size of  $n = 540$  boys and  $n = 540$  girls per arm would have 95% power to detect an effect separately for each gender (two-sided,  $\alpha = 0.05$ ). To account for 10% loss, the sample size will be inflated by  $(540/10 =) 54$  of each gender per arm, and to account for 10% loss within this additional recruitment, a further inflation of  $(54/10 =) 6$  to give a target sample size of 600 boys and 600 girls per arm, totalling 1,200 per arm (intervention versus control). Therefore, a total of 2,400 students will be recruited. Students will be equally divided across years 6, 7, and 8, and gender.

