### 6.1 Primary outcome

The primary outcome of body image will be measured using the Body Esteem Scale for Adults and Adolescents. The BESAA is comprised of three subscales (*Appearance, Weight and Attribution*) and asks participants about their thoughts and feelings in relation to their body and appearance. Responses to items will be indicated using a 5-point Likert scale, ranging from 1 (*Never*) to 5 (*Always*), with higher scores indicating greater dissatisfaction. Only the combined mean scores for the Appearance and Weight subscales will be used in analyses, as the Attribution subscale relates to the perception of others' attitudes towards one's appearance. The English language BESAA has demonstrated good internal and re-test reliability and construct validity among Indian adolescents and other globally diverse adolescent samples. A Hindi version of the scale will be used in this study.

Table 4.1 summarises the descriptive statistics that will be extracted for BESSA. These data will be further summarised graphically using box-and-whisker plots, error bar graphics, scatterplots and similar as appropriate. Effect size will be calculated using Cohen's *d* and 95% confidence intervals for Cohen's *d* will also be given. Percentages reporting positive change, no change, and a poorer outcome, along with 95% confidence intervals will be reported.

The primary analysis will be a linear mixed model with random intercepts with school declared as a random factor. The model will additionally include the three main effects, three two-way interactions, and the three-way interaction for randomised arm (between subjects fixed effect factor with 2 levels comic intervention and control), study phase (repeated measures fixed effect factor with two levels T2 and T3), gender (between subjects fixed effects factor with 2 levels, male and female) and include a baseline measure as a covariate, and the three two-way interactions between covariate and each of randomised arm, gender, and phase). An overall assessment of the contribution of randomised arm to the model will be undertaken using the change in the log-likelihood statistic between its inclusion and exclusion from the model. Post hoc analyses will proceed primarily comparing the two randomised arms at T2 controlling for baseline covariate

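### The mixed models leave out both minimisation factors; adding them together with a small-sample test of arm could gain precision at little cost

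*SAP*

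**What the plan says.** Schools are the unit of randomisation. Section 3 states: "The minimisation factors are (i) number of students at grade 6, 7 or 8 and (ii) proportion of boys", both counted over grades 6 to 8. On the mechanism it adds: "The first 8 schools will be allocated using blocked randomisation thereafter probabilistic minimisation will occur with the probability of minimising set to 0.8".

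Section 4.1 makes the primary endpoint a T2 comparison: "significant differences in body esteem between randomized groups at T2 after controlling for baseline measure of body esteem".

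Section 6.1 (Primary outcome) sets the model: "The primary analysis will be a linear mixed model with random intercepts with school declared as a random factor". The fixed part is listed term by term: arm, phase and gender with all their interactions, and then "include a baseline measure as a covariate, and the three two-way interactions between covariate and each of randomised arm, gender, and phase". School size and school proportion of boys are not in the list. Arm is assessed "using the change in the log-likelihood statistic between its inclusion and exclusion from the model", and no small-sample correction is named. The T2 comparison follows as a further step: "Post hoc analyses will proceed primarily comparing the two randomised arms at T2 controlling for baseline covariate". The section on secondary outcome measures applies the same plan to all of them.

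Section 5 adds: "The model will additionally include school as a random factor, and a sensitivity analysis relating to the inclusion-exclusion of this effect will be conducted". That sensitivity analysis concerns the school effect, not the minimisation factors. The SAP plans no analysis that includes those factors.

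**The concern.** Minimisation makes the arms more alike on its factors than chance would. If the factors also predict a school's outcome, the true sampling variation of the arm difference shrinks. A model without them leaves their variance in the school effect, so the standard error it reports does not shrink. A test that is otherwise correctly sized then rejects too rarely under the null and has less power than the design could give.

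Pupil gender and baseline score are already in the model and may absorb part of what the factors predict, especially proportion of boys. Pupil gender is not the same variable as a school's gender mix, though, and nothing in the model stands for school size. What is at stake is precision in a trial whose arm comparison rests on the number of schools.

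**Working it through.** **Inputs from the SAP.** d = 0.2; two-sided alpha 0.05; 4 × 540 = 2,160 pupils analysed (Section 5); allocation as in Section 3. The power figure in Section 5 does not involve schools, so the SAP has no figure on this point to reproduce.

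**Assumptions, because the SAP is silent.** 12, 20 or 40 schools (J); ICC of 0.02 or 0.05 after baseline and gender; 0, 10 or 30% of between-school variance explained by the two factors.

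**Step 1: mechanism by hand (equal schools, SD 1).** A school mean has variance V = ICC + (1 − ICC)/m with m = 2,160/J, and the arm contrast has SE = √(4V/J). For J = 20 and ICC 0.05, m = 108:
- Without the factors: V = 0.05 + 0.95/108 = 0.0588; SE = √(4 × 0.0588/20) = 0.108.
- With factors explaining 30%: V = 0.7 × 0.05 + 0.0088 = 0.0438; SE = 0.094.

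The model without the factors reports about 0.108 however well allocation has balanced them.

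**Step 2: simulation.** 5,000 trials per cell at pupil level, with unequal schools (size CV about 0.47). The first 8 schools are in one 4:4 block (block size assumed), then minimisation with probability 0.8. The factors are split at the median size and at half boys (also assumed). The T2 model has a random school intercept and is fitted by REML, with J − 2 degrees of freedom without the factors and J − 4 with them, as a stand-in for Kenward-Roger.

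At J = 20, ICC 0.05 and 30% explained, the model without the factors reports SE 0.111 against an actual 0.101, so about a tenth too large. With the factors it is 0.098 against 0.099. At 0% explained the model without them is right: 0.110 against 0.111.

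Power (%) of the T2 arm contrast, without → with the factors:

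| Schools | ICC | 0% explained | 10% | 30% |
|---|---|---|---|---|
| 12 | 0.02 | 48.7 → 41.6 | 47.5 → 44.7 | 47.3 → 51.6 |
| 12 | 0.05 | 26.0 → 22.5 | 26.2 → 24.4 | 23.8 → 28.4 |
| 20 | 0.02 | 67.3 → 65.6 | 69.1 → 69.4 | 68.7 → 75.1 |
| 20 | 0.05 | 40.5 → 38.9 | 40.8 → 42.1 | 39.8 → 48.8 |
| 40 | 0.02 | 85.8 → 85.4 | 86.8 → 87.7 | 87.9 → 91.1 |
| 40 | 0.05 | 64.1 → 63.5 | 64.1 → 66.3 | 66.5 → 74.3 |

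Type I error of this small-sample test without the factors is 5.0–5.6% (0% explained), 4.4–5.0% (10%) and 3.1–4.2% (30%). With them it is 4.7–5.6% throughout. Interpolated break-even is about 16–18% explained with 12 schools, 5–9% with 20 and 2–3% with 40.

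A separate check on school means agrees. With 24 schools, ICC 0.02 and 25% explained, type I error is 3.6% without and 5.4% with the factors, and power is 76% and 81%.

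**Step 3: the test the SAP names.** For one arm term in a regression of school means, the change in twice the log-likelihood is J·ln(1 + t²/df). Referred to chi-squared on 1 df, it rejects when t² > df·(e^(3.841/J) − 1). With non-prognostic factors:
- J = 12, without: df 10, |t| > 1.942, type I error 8.1%. With: df 8, |t| > 1.737, 12.1%.
- J = 20, without: df 18, |t| > 1.952, 6.7%. With: df 16, |t| > 1.841, 8.4%.
- J = 40, without: df 38, |t| > 1.957, 5.8%. With: df 36, |t| > 1.905, 6.5%.

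Simulations of the single term with the factors added give about 10–13% with 12 schools, 7–9% with 20 and 6–7% with 40. For the joint test of all five arm terms in the Section 6.1 model (arm, arm by phase, arm by gender, the three-way term, arm by baseline):

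| Schools | Without the factors | With the factors |
|---|---|---|
| 12 | 5.6–6.6% | 8.0–8.6% |
| 20 | 5.0–6.3% | 6.2–7.2% |
| 40 | 4.4–5.9% | 5.1–6.4% |

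**The case against.** A reader might infer that the test planned in the SAP is conservative because the factors are left out. The SAP does not support that. Its stated test is a log-likelihood change with no correction named, and with few schools that test is somewhat liberal. Without the factors, the single-term version runs at 5.4–8.7% with 12 schools, and at 6.0–7.0% with 20 if the factors explain 0 to 10%. It falls clearly below 5% only with 20 or 40 schools and 30% explained (3.3–4.8%). This objection stands, and it is why the covariates and the test have to change together.

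Three further objections have weight. First, the gain depends on a prognostic strength that the SAP does not give; with about a dozen schools and weak factors, adjustment loses power. Second, the first 8 schools are allocated by blocks, so with few schools the balance to be exploited is only partial. Third, the point may not reach the primary endpoint as planned. The T2 comparison is described as a post hoc ANCOVA, and the SAP does not say whether it has a school term. Without one, simulated type I error is 17–56% over the assumed settings, so the error there is in the opposite direction. The point likewise does not apply to the sensitivity analysis without the school effect or to the ordinal and binary logistic models, which list no school term.

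None of this removes the omission. The SAP itself lists the model in full, so the choice is not one left to another document.

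**Conclusion.** The point holds as an optional improvement. Two factors judged important enough to steer allocation are absent from the primary and secondary mixed models, without explanation. The consequence is possible lost precision in a correctly sized, school-level test of arm. It is not bias, and the omission does not inflate type I error.

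Over 12 to 40 schools and ICC 0.02 to 0.05, the paired change is worth about +3 to +10 points of power if the factors explain 30% of between-school variance after baseline and gender, and about -7 to +2 points if they explain 0 to 10%. Number of schools, ICC and prognostic strength are all assumptions, so the range matters more than any single cell. The direction is well supported; confidence in the size is moderate.

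**What to change.** Make one paired change in Section 6.1, carried to the secondary outcomes:
- Add number of students and proportion of boys in grades 6 to 8 as fixed school-level covariates, in the form used in the allocation. State that form, since Section 3 does not say whether the factors are categorised.
- Take the T2 arm contrast from that mixed model, with school as a random effect.
- Test it by REML with Kenward-Roger or Satterthwaite degrees of freedom, in place of the uncorrected change in log-likelihood.

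The first step should not be taken without the third. If only about a dozen schools are randomised, decide before outcome data are seen whether to keep the factors, and record the reason.

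The cost is a few sentences in the SAP, and the school data are already needed for allocation. It is more than a covariate change, because it also replaces the stated test and fixes which model supplies the T2 result. The statistical price is two between-school degrees of freedom: at most about 2 points of power with 20 or more schools, and up to about 7 with 12 if the factors turn out not to be prognostic.

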### 4 Endpoints

#### 4.1 Primary Endpoint:

To assess whether there are significant differences in body esteem between randomized groups at T2 after controlling for baseline measure of body esteem.

#### 4.2 Secondary Endpoints:

The data analysis plan for the primary outcome measure will be the same plan for all secondary outcome measures.

- (a) To assess changes in all outcome measures and their subscales over the study duration (between T1, T2, and T3) within each randomised arm.
- (b) To assess whether outcomes measures at T2 differ between randomised arms after controlling for commensurate baseline scores
- (c) To assess whether outcomes measures at T3 differ between randomised arms after controlling for commensurate baseline scores
- (d) To assess whether outcome measures change between T2 and T3 and whether any changes are dependent on randomised arm after controlling for commensurate baseline scores
- (e) To assess whether any differences in measures at T2 between randomised arms are gender specific after controlling for commensurate baseline scores
- (f) To assess whether any differences in measures at T3 between randomised arms are gender specific after controlling for commensurate baseline scores
- (g) To assess whether interventional changes in Body Esteem between T1 and T3, and Body Esteem at T3, are mediated by changes in internalisation of appearance ideals between T1 and T2, and whether mediation is gender dependent.

## Statistical Analysis Plan

---

### 5 Sample Size

The study design comprises two independent groups with data collected at three time points (T1, T2, T3). The resulting data is amenable to standard analysis for two group comparisons including a 2 by 2 by 2 by mixed factorial design with randomised group as a two level between subjects fixed factor, trial phase (T2, T3) as a longitudinal two-level repeated measures factor, gender as a two-level fixed factor and with commensurate baseline measure (T1) as a mean adjusted covariate. This may be assessed as a classic factorial ANCOVA for a 2 by 2 by 2 mixed design or using a random intercepts mixed linear model capturing the full factorial structure. The model will additionally include school as a random factor, and a sensitivity analysis relating to the inclusion-exclusion of this effect will be conducted

The evaluation of *Confident Me* in an urban Indian setting indicated a range of effect sizes for outcome measures with standardized effects in the small to medium range and exceeding an effect size of  $d = 0.2$ , which would minimally be of interest to public health policy makers. For a lower bound of  $d = 0.2$ , a sample size of  $n = 540$  boys and  $n = 540$  girls per arm would have 95% power to detect an effect separately for each gender (two-sided,  $\alpha = 0.05$ ). To account for 10% loss, the sample size will be inflated by  $(540/10 =) 54$  of each gender per arm, and to account for 10% loss within this additional recruitment, a further inflation of  $(54/10 =) 6$  to give a target sample size of 600 boys and 600 girls per arm, totalling 1,200 per arm (intervention versus control). Therefore, a total of 2,400 students will be recruited. Students will be equally divided across years 6, 7, and 8, and gender.

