## Statistical Analysis Plan

---

sensitivity analysis will be undertaken to better understand the data. As appropriate, missing data sensitivity analyses will be performed on both the ITT **analysis** set and the PP **analysis** set.

In general, all statistical tests will be performed as two-sided tests with a nominal significance level of  $\alpha = 0.05$  and effect sizes reported.

There is no planned interim analysis for trial progression but there will regular reports to the trial steering committee and trial management group for oversight.

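### The SAP plans a sensitivity analysis that drops school, the unit of randomisation, and does not state a school term for the T2/T3 ANCOVAs or the logistic models

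*SAP*

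**What the plan says.** Section 3 makes the school the unit of allocation: "Participants will be randomized to either the intervention or control arm at the school level". The reason given is contamination: "Randomization will be conducted at the school level to avoid potential spill over effects within a school".

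Section 5 (Sample Size) describes the factorial structure of the data and says "This may be assessed as a classic factorial ANCOVA for a 2 by 2 by 2 mixed design", with a random-intercepts mixed model as the other form. It then adds school to the model as a random factor and states that "a sensitivity analysis relating to the inclusion-exclusion of this effect will be conducted".

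Section 6.1 (Primary outcome) names the primary analysis: a random-intercepts linear mixed model in which school is a random factor. The overall role of arm is judged by a change in log-likelihood. The arms are then compared at T2, and again at T3, in post hoc analyses, which the same section goes on to call ANCOVA. No school term is stated for these. Section 4.1 defines the primary endpoint as the baseline-adjusted difference between arms at T2, so it is one of these post hoc comparisons that addresses it directly. Sections 4.2, 6 and 6.1 (Secondary Outcome measures) carry the plan over to the secondary outcomes.

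Section 6.2 lists three terms for the ordinal and binary logistic models: baseline value, arm and gender. School is not among them.

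**The concern.** A sensitivity analysis should vary an assumption that could reasonably be otherwise. Allocation by school is a fact of the design. An analysis without school treats pupils as if each had been randomised separately, and for the overall arm effect its standard error is too small whenever pupils in the same school resemble one another. Agreement with the primary model therefore says little about robustness, and disagreement would tend to come from the no-school version being over-significant.

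The wording in section 5 would matter less if every other between-arm test clearly kept school. The T2 comparison that addresses the primary endpoint is described only as a post hoc ANCOVA, and the logistic models are listed without school. An analyst following the text could fit these without any allowance for clustering and still be within the plan.

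**Working it through.** **The plan's own figure.** Section 5 gives 540 per gender per arm for d = 0.2, two-sided alpha 0.05 and 95% power. With no clustering term, n = 2 × (1.960 + 1.645)² / 0.2² = 650, and 540 gives 90.8% power. The 540 therefore does not reproduce from its stated inputs. That is a separate matter; here 540 serves only to fix the number analysed.

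**Inputs**
- Pupils analysed: 4 × 540 = 2,160 (section 5, the target before inflation for 10% loss).
- Nominal two-sided alpha 0.05 (section 6).
- Number of schools J: not in the SAP; assumed 16, 24 and 40. Section 3 implies only that more than 8 are expected, since minimisation starts after the first 8.
- ICC: not in the SAP; assumed 0.01, 0.02 and 0.05. The relevant value is the one left after baseline adjustment.

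**Formulae**
- Pupils per school: m = 2,160 / J, taking equal school sizes.
- Design effect: DE = 1 + (m − 1) × ICC.
- True type I error of a nominal 5% test that ignores school: 2 × [1 − Φ(1.96 / √DE)].

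**Example.** With J = 16, m = 135. At ICC 0.02, DE = 1 + 134 × 0.02 = 3.68, 1.96 / √3.68 = 1.02, and the type I error is 0.31.

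**Whole-sample test of arm without school**

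| Schools (m) | ICC 0.01 | ICC 0.02 | ICC 0.05 |
|---|---|---|---|
| 16 (135) | DE 2.34, 20% | DE 3.68, 31% | DE 7.70, 48% |
| 24 (90) | DE 1.89, 15% | DE 2.78, 24% | DE 5.45, 40% |
| 40 (54) | DE 1.53, 11% | DE 2.06, 17% | DE 3.65, 31% |

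At ICC 0.005 the range over 16 to 40 schools is still 8-13%.

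**Single-gender test.** In mixed schools m is halved (1,080 / J). Over 16 to 40 schools the type I error is 8-13% at ICC 0.01, 11-20% at 0.02 and 20-35% at 0.05.

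**Where school stands in each between-arm analysis**

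| Analysis | SAP section | School term |
|---|---|---|
| Primary mixed model | 6.1 Primary outcome | Stated, random |
| Sensitivity analysis | 5 | Removed in one version |
| Post hoc T2 and T3 ANCOVA | 6.1 Primary outcome | Not stated |
| Ordinal and binary logistic models | 6.2 | Not in the list of terms |

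**The case against.** The strongest reply is that the SAP already ranks the analyses. Section 6.1 names the mixed model with school as primary, and section 5 itself says the model will include school and calls its exclusion a sensitivity analysis. This stands. A reader might infer from section 5 that the primary model is still open between ANCOVA and a mixed model, or that nothing says which result takes precedence. The documents do not support that: the ANCOVA wording is background in the sample size section, and section 6.1 supersedes it for the primary model.

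The error rates describe only a test without school and rest on assumed ICCs and school counts. This also stands. They say nothing about the error rate of the primary mixed model.

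It may also be said that dropping school does not always make a result look stronger. That is correct for contrasts within schools, such as arm by gender where schools contain both sexes: there, school variance moves into the residual and the test can become weaker. If the estimated school variance is zero, the two versions agree. The point is therefore limited to the overall arm contrast and its single-gender counterparts.

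Finally, a comparison with and without school can be used descriptively, and section 5 does not say that a conclusion will be drawn from the no-school result. That is fair, and no intention to report it selectively should be inferred. But the SAP does not label it descriptive either. If conclusions prove sensitive to the data set and approach, section 6 offers only a further sensitivity analysis.

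On the post hoc ANCOVAs, the SAP is silent rather than explicit. A reader might infer that they will certainly omit school. The text does not say so; it leaves the matter unfixed.

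**Conclusion.** The point holds in a limited form. The primary model is correctly specified with school random. The planned analysis without school is not a valid test of the overall arm effect. Under the assumptions of 2,160 pupils, equal school sizes and 16 to 40 schools, its type I error would be about 11-20%, 17-31% and 31-48% at ICC 0.01, 0.02 and 0.05, and lower for single-gender tests. The same inflation would affect any T2 or T3 ANCOVA fitted to the whole sample without school. The logistic models raise the same problem, although the figures were not computed for an ordinal outcome.

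The SAP should be changed, because the comparison that addresses the primary endpoint is among those with no stated school term. The defect is not fatal, because the named primary analysis respects the randomisation.

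**What to change.** 1. In section 5, remove the school-exclusion sensitivity analysis, or label it descriptive only, with no inference drawn from it. Remove the ANCOVA alternative there, so that section 5 agrees with section 6.1.
2. State once, in section 6, that every between-arm test accounts for school whatever the estimated school variance. Name the T2 and T3 contrasts and the ordinal and binary logistic models explicitly.
3. If a check on clustering is wanted, analyse baseline-adjusted school means by arm, with degrees of freedom equal to the number of schools minus 2.
4. Report the ICC with its confidence interval.

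The cost is SAP wording and one simple school-level analysis. No new data are needed. Intervals will be somewhat wider wherever school would otherwise have been left out.

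### The stated 95% power for each gender is about 91% on the SAP's own inputs (d = 0.2, 540 per gender per arm, two-sided 0.05)

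*SAP*

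**What the plan says.** Section 5 (Sample Size) takes d = 0.2 as the smallest effect of interest and states that 540 boys and 540 "girls per arm would have 95% power to detect an effect separately for each gender (two-sided", alpha 0.05). It adds 54 and then 6 per gender per arm for 10% loss, which gives 600 per gender per arm and 2,400 pupils in total. The section gives no baseline-outcome correlation, no T2-T3 correlation, no intraclass correlation (ICC) and no cluster size.

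The other places that bear on this are:

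- Section 6 (Analysis Plan) confirms the sidedness: "all statistical tests will be performed as two-sided tests with a nominal significance level of" 0.05.
- Section 4.1 sets the primary endpoint as "significant differences in body esteem between randomized groups at T2 after controlling for baseline measure of body esteem", which is a comparison of whole arms.
- Section 6.1 (Primary outcome) lists comparisons split by gender among the post hoc analyses at T2 and T3, and section 6.3 names gender as the only subgroup.
- Section 3 makes the school the unit of allocation: "Randomization will be conducted at the school level to avoid potential spill over effects within a school".

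**The concern.** Section 5 gives every input of a standard two-group power calculation, and the result does not follow from them. The shortfall of about 4 percentage points is too large to come from rounding or from the choice between a normal and a t formula.

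Power within each gender is the only stated basis for 540, and so for 600 and 2,400. On the printed inputs, the chance of missing d = 0.2 in one gender is about 9%, not 5%. A null result in boys or in girls would then be read against a power that the stated calculation does not deliver.

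**Working it through.** **Inputs (section 5):** d = 0.2, so SD = 1; n = 540 per group within one gender; alpha = 0.05 two-sided; stated power 95%. Allocation is 1:1 (section 1).

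**1. The plan's figure.** The noncentrality is d × √(n/2) = 0.2 × √270 = 3.286.

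- Normal approximation, two-sided: Φ(3.286 − 1.960) = Φ(1.326) = 90.8%.
- Exact noncentral t, two-sided: 90.7%.

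The stated 95% is not reproduced.

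**2. Sample size for 95%, two-sided.** n = 2 × (1.960 + 1.645)² / 0.2² = 649.7, so 650 by the normal formula. The noncentral t gives 94.98% at 650 and passes 95% at 651. At 600 per group (everyone recruited, no loss) power is 93.3%.

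**3. Effect detectable with 95% power at 540.** d = (1.960 + 1.645) × √(2/540) = 0.219 (noncentral t: 0.2196), so about 0.22.

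**4. Which calculation gives 95%?** A one-sided 5% test gives Φ(3.286 − 1.645) = 95.0% (noncentral t: 94.9%) and needs 542 per group for 95%. The match is close, but the SAP does not say that this was done.

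**5. Could an unstated variance reduction explain it?**

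- Baseline adjustment multiplies the variance by 1 − r². At 540, 95% needs r of at least about 0.41. By the normal formula, r = 0.3 gives 93.1%, r = 0.4 gives 94.8% and r = 0.5 gives 96.7%.
- Averaging T2 and T3 multiplies the variance by (1 + ρ)/2. Reaching 95% needs ρ of at most about 0.66. The primary endpoint is at T2 alone.

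**6. Pooled T2 comparison.** With 1,080 per arm on the same independent-pupil basis, power is 99.6%.

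**7. Illustration of school clustering.** The SAP gives no ICC or cluster size, so the values here are assumed: m analysed pupils of one gender per school, and effective n = 540 / (1 + (m − 1) × ICC). For example, m = 30 and ICC = 0.01 give 540/1.29 = 419. Power within one gender at d = 0.2, with no baseline adjustment, is:

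| m | ICC 0.01 | ICC 0.02 |
|---|---|---|
| 20 | 85% | 80% |
| 30 | 82% | 74% |
| 40 | 80% | 69% |

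**The case against.** The strongest reply is that an unadjusted t-test is not the planned analysis. Section 5 itself, just before the power sentence, describes an ANCOVA or mixed model with the T1 score as covariate, and sections 4 and 6.1 also adjust for baseline. If d = 0.2 is on the raw SD scale, a moderate correlation restores 95%. Adjustment also softens the clustering illustration: with r = 0.5 the 69% to 85% range becomes about 81% to 94%.

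This is fair as far as it goes. Neither 5% nor 9% is the miss rate of the planned model, since adjustment raises power and clustering lowers it. But section 5 states no correlation and does not say that one was used. If d = 0.2 is already the adjusted effect, the covariate does not rescue the figure. A reader cannot credit an assumption that is not written down.

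Two further points are right and limit the finding. The missing ICC is a separate matter from this arithmetic slip, and the clustered figures are illustrations that carry no weight in showing the error. The comparisons split by gender are post hoc, and the primary comparison is barely affected. Section 4.2(e), on whether "differences in measures at T2 between randomised arms are gender specific after controlling for commensurate baseline scores", reads more naturally as an arm-by-gender question than as the within-gender test that was powered.

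**Conclusion.** The sentence is wrong as written. Its inputs give 90.7% power in each gender, and 540 is about 17% below the 651 that two-sided 95% requires (540/651 = 0.83). This conclusion needs nothing from outside section 5. It assumes independent pupils and no baseline adjustment, as the printed inputs imply. A one-sided calculation labelled two-sided is the likely cause, but that is inference.

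The slip should be fixed because the whole recruitment target is derived from it. It does not by itself threaten the pooled T2 primary comparison, and it does not call for more pupils. The true power of the planned school-level analysis cannot be worked out from the SAP, because it gives neither the baseline correlation nor the ICC and cluster size.

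**What to change.** Keep the target of 540 analysed and 600 recruited per gender per arm, and replace the power sentence in section 5 with wording such as:

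> For d = 0.2, 540 boys and 540 girls per arm give about 91% power in each gender (95% for d = 0.22), two-sided alpha 0.05, assuming independent pupils and no baseline adjustment. Allowing for randomisation by school, with an assumed ICC of [value] and [m] analysed pupils of one gender per school (design effect 1 + (m − 1) × ICC), power is [value].

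The trial team must supply the bracketed values. If 95% did rest on baseline adjustment or on averaging T2 and T3, state the assumed correlation and show that calculation instead, again with the school design effect.

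The cost is one recalculation and a change of SAP wording. The stated power becomes less favourable, more so once the design effect is shown. No pupils are added, and no model or test changes.
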